#### **Onset timing of adverse reactions**

Adverse reactions will be summarized by timing of first onset [<26 weeks,  $\geq$ 26 to <52 weeks,  $\geq$ 52 to <78 weeks,  $\geq$ 78 to <104 weeks,  $\geq$ 104 to <156 weeks,  $\geq$ 156 weeks] for each SOC and PT in terms of n and proportion. When calculating the proportion, the denominator will be the number of patients in each category of onset time who received at least one dose.

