7.2.4. Observation period

3 years from the first day of treatment with this drug (156 weeks) However, the observation period for patients who started to receive this drug after May 2018 will be 1.5 years (78 weeks).

> Pfizer Confidential Page 12 of 37

If the treatment with this drug is discontinued during the observation period, the observation period will be until the day of discontinuation. If the dose of this drug is changed for the treatment of ATTR-CM, the observation period will be up to the date of last dose of 20 mg.

This study will be conducted using booklet type CRF.

The safety and efficacy assessments will be performed at the first visit (including the end date of the observation period) on or after the end date of the observation period (day of discontinuation if the treatment is discontinued during the observation period or date of the last dose of 20 mg if the dose was changed for the treatment of ATTR-CM). However, if a subject is lost to follow-up halfway through, the safety and efficacy assessments will be performed using the information on the last visit date.

Booklet No.	Observation period	
Booklet 1	First day of treatment to Week 78 (1.5 years)	
Booklet 2	Week 79 to Week 156 (3 years)	

7.3. Registration items and study items This study will be conducted according to the following schedule of observation.

Table 1. Schedule of observation

			Booklet 1		Book	det 2
Item	Registr ation form	At start of the study	Week 52 (1 year)	Week 78 (1.5 years)	Week 104 (2 years)	Week 156 (3 years)
Information to identify the subject			-	-	-	-
First day of treatment with this drug			-	-	-	-
Presence or absence of having received/used this drug at other sites, and if Yes, patient's duration of treatment	•					
THAOS registration status/THAOS registration ID						
State of concurrent medical examination	-					→
Background variables	-		-	-	-	-
History of previous treatment drugs for the targeted disease	-	•	-	-	-	-
Targeted drug use record	-	•				>
Concomitant therapy (drug therapy/ non-drug therapy)	-	•				
General tests (height, body weight, pulse, blood pressure)	-	•				
Clinical laboratory tests	-	•				→
Plasma concentration of tafamidis (to be performed only for patients with severe hepatic impairment)	-					•
Cardiovascular evaluation (ECG, echocardiography)	-					
Assessment of neurological function (NIS)	-		-		-	
Quality of Life (QOL-DN)	-		-		-	
Ambulatory state	-		-		-	

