## [Rationale for sample size]

On the basis of the review of data on patients with familial amyloid polyneuropathy who were registered in the database from the Amyloidosis Clinical Survey Forms of the Specific Diseases Treatment Research Program by the Ministry of Health, Labour and Welfare for 3 years from 2003 to 2005, it is reported that the number of patients with familial amyloid polyneuropathy is 64 to 88 patients/year, and the estimated prevalence of familial amyloid polyneuropathy in Japan is 0.87 to 1.1 per population of 1 million people after the number of patients was corrected and calculated from the acquisition rate of data 1). When this

> PFIZER CONFIDENTIAL Page 13

prevalence is multiplied by the Japanese population (127.54 million, as of November 2012), the estimated number of patients with TTR-FAP (hereinafter referred to as this disease) is approximately 111 to 140. On the website of the Japan Intractable Diseases Information Center, the estimated annual number of patients treated for this disease is approximately 130 on the basis of the nationwide epidemiological survey conducted in 1991. As described above, considering that this disease is a rare disease and the safety and efficacy information of this drug based on Japanese clinical studies are limited, all patients who received/used this drug will be collected as much as possible.

Planned period covered by this study

Duration of study: November 2013 to May 2021 (7.5 years)

Registration period: November 2013 to November 2019 (6 years)

A contract will be concluded after the start date of the study period, and then, the patient registration will be started.

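### Onset-timing table: patients who already had a reaction stay in the first-onset denominator, and a 52-week class sits beside 26-week classes with no time unit

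*SAP*

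**What the plan says.** SAP 8.2.3.1, under Onset timing of adverse reactions, defines the table as follows.

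- Numerator: "Adverse reactions will be summarized by timing of first onset". A patient therefore counts once per term, in the class of the first occurrence.
- Rows and statistics: "for each SOC and PT in terms of n and proportion".
- Classes: <26, 26 to <52, 52 to <78, 78 to <104, 104 to <156 and ≥156 weeks. The first four are 26 weeks wide, the fifth is 52 weeks and the last is open.
- Denominator: "the denominator will be the number of patients in each category of onset time who received at least one dose". The revision history shows that this definition was added in SAP version 10.0.

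Protocol 7.2.4 sets the follow-up. The standard period is 156 weeks, but "the observation period for patients who started to receive this drug after May 2018 will be 1.5 years (78 weeks". Stopping the drug ends observation: "If the treatment with this drug is discontinued during the observation period, the observation period will be until the day of discontinuation".

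SAP section 4 lists no hypotheses and no decision rules.

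**The concern.** A first-onset proportion for an interval is a conditional risk only if its denominator holds the people who could still have a first onset. The SAP sentence is loosely worded. On its natural reading it counts everyone dosed during the interval, including those whose first onset fell earlier. Those patients dilute every class after the first, and the dilution grows with time.

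The unequal widths are a second, separate problem. A 52-week class collects about twice the first onsets of a 26-week class at the same underlying rate, and the two proportions stand side by side with no time unit.

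The stated objective is safety in long-term use, and the final analysis supports reexamination. A reader will naturally use this table to ask whether reactions become more or less frequent with continued treatment, and neither feature lets the columns be compared directly.

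**Working it through.** The plan gives no figure for this table, so there is none to reproduce.

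**Inputs from the documents**
- Class limits a to b: 0, 26, 52, 78, 104, 156 weeks (SAP 8.2.3.1).
- Cohort scale: "the estimated number of patients with TTR-FAP (hereinafter referred to as this disease) is approximately 111 to 140" (SAP, rationale for sample size). This agrees with 0.87 × 127.54 = 111.0 and 1.1 × 127.54 = 140.3. It is a prevalence estimate, not a recruitment target.

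**Assumptions, not in the documents**
- Constant hazard, with 3-year risk R of 5%, 10%, 20%, 30% or 50% for a given row.
- No discontinuation in the base case.

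**Formulas**
- λ = −ln(1 − R)/156 per week; S(t) = exp(−λt).
- Proportion as planned: S(a) − S(b).
- Proportion with an event-free denominator: [S(a) − S(b)]/S(a).
- Relative understatement: 1 − S(a), whatever the class width.
- First-onset rate: 5,200 × λ per 100 patient-years at risk, the same in every class.

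**Example, R = 30%.** λ = 0.3567/156 = 0.002286. S at 26, 52, 78, 104 and 156 weeks is 0.942, 0.888, 0.837, 0.788 and 0.700. The rate is 11.9 per 100 patient-years throughout.

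| 3-year risk | As planned, %: four 26-week classes, then 104 to <156 | Event-free denominator, %: each 26-week class, then 104 to <156 | Understatement in 104 to <156 |
|---|---|---|---|
| 5% | 0.85, 0.84, 0.84, 0.83, 1.64 | 0.85, 1.70 | 3% |
| 10% | 1.74, 1.71, 1.68, 1.65, 3.22 | 1.74, 3.45 | 7% |
| 20% | 3.65, 3.52, 3.39, 3.27, 6.18 | 3.65, 7.17 | 14% |
| 30% | 5.8, 5.4, 5.1, 4.8, 8.8 | 5.8, 11.2 | 21% |
| 50% | 10.9, 9.7, 8.7, 7.7, 13.0 | 10.9, 20.6 | 37% |

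**Separating the two effects.** The step from 78 to <104 into 104 to <156 is a factor of 1.64/0.83 ≈ 1.98 at 5% risk and 8.84/4.83 = 1.83 at 30%. With the event-free denominator alone, the 30% step is 11.21/5.77 = 1.94, which is larger. The step therefore comes from class width, and the dilution partly hides it. Splitting at Week 130 with the event-free denominator gives 5.8% in both halves at 30% risk.

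**Discontinuation**
- Stopping unrelated to the reaction leaves the understatement at 1 − S(a). A separate run with a constant 10% risk per 26 weeks and 10% stopping per 26 weeks gave 9.5, 8.6, 7.7, 6.9 and 11.3% as planned. The event-free denominator gave 9.5% four times and then 17.2%. The rate was 21.1 per 100 patient-years in every class.
- If a share s of patients with the reaction stop because of it, the planned denominator becomes 1 − s[1 − S(a)]. With s = 0.5 and 30% risk, the 104 to <156 denominator is 1 − 0.5 × 0.212 = 0.894. The understatement is then 1 − 0.788/0.894 = 12% instead of 21%; at 20% risk it is 7% instead of 14%. With s = 1 it is zero. The width effect remains in every case.

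**In patients.** With 140 patients, 30% risk and no dropout, the fall from 5.8% to 4.8% is 140 × 0.0577 = 8.1 against 140 × 0.0483 = 6.8 expected first onsets. The exact 95% interval for 8/140 is 2.5% to 10.9%.

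**The case against.** Much of the case on the other side stands.

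- The width is printed in the column heading, and a proportion over a labelled 52-week interval is a correct statement about that interval. This stands, but the reader still has to do the conversion.
- The drift is small here: about one patient over two years at 140 patients and an assumed 30% risk, well inside chance variation. The SAP asks for rows by SOC and PT and mentions no any-reaction row, so a 30% row would have to be a common SOC. For rare terms the dilution cannot be seen. This stands.
- Patients who stop because of a reaction leave later denominators, so the base-case percentages are the upper end for each assumed risk. This stands. However, the SAP's action-taken categories include temporary interruption and no change, so universal stopping cannot be presumed.
- The sentence already deals with a larger problem. If it is built from dosing dates, dropouts and the 78-week cohort do not dilute later classes. This also stands.

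A reader might infer that the denominator creates both a false decline and a false late rise. The arithmetic does not support that: the rise is due to width alone, and correcting the denominator by itself makes the step larger. A reader might also infer that this is the only table bearing on reactions and length of use. SAP 5.4 and 8.2.3.3 also tabulate reactions by duration of treatment, although not by time at risk, and some safety text is redacted. No such claim can be made.

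**Conclusion.** The point holds as a minor, inexpensive improvement. As written, the table keeps patients with an earlier onset in a first-onset denominator. The resulting understatement is 1 − S(start of interval): in the 104 to <156 week class, about 14% at 20% 3-year risk and 21% at 30%. These figures assume a constant hazard and no reaction-related stopping; they are smaller if patients with reactions stop, and negligible for rare PTs. Separately, the double-width class nearly doubles the proportion at low rates even though the hazard has not changed.

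The documents do not support saying that a constant risk will in general visibly fall and then jump. The fall is noticeable only for common SOC rows and lies within chance variation at this cohort size. No hypothesis, error rate or decision rule is touched; only the reading of the time pattern is affected.

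**What to change.** In SAP 8.2.3.1, define the denominator for each SOC/PT row and interval as patients on treatment and still free of that SOC/PT reaction at the start of the interval. Add the number of first onsets per 100 patient-years at risk for each interval, or else split 104 to <156 at Week 130. The denominator change removes the dilution, and the rates or the split remove the width effect; neither change does both. Rates are preferable because they also allow for patients who stop partway through a class and for the little planned follow-up in the open ≥156-week class.

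The cost is a sentence or two in the SAP and minor programming, since onset dates and treatment dates are already collected (Protocol 7.3.2.12 and 7.3.2.6). There is a small downside: denominators will differ by row, so the table loses a common N per column. Showing the number of patients dosed in each interval alongside keeps it easy to reconcile.

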## Association between pretreatment and adverse reactions

To examine the association between a pretreatment and adverse reactions, patients with any adverse reaction will be summarized by pretreatment in terms of n.

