#### 5.4. Subgroups

Subgroup analyses for safety and efficacy will be performed with respect to the following factors:

- Patient characteristics
  - Sex [male, female]
  - Age [ $<15 \text{ yrs.}, \ge 15 \text{ to } <65 \text{ yrs.}, \ge 65 \text{ yrs.}$ ]
  - Body weight [ $\leq 50 \text{ kg}$ ,  $\geq 50 \text{ to } \leq 60 \text{ kg}$ ,  $\geq 60 \text{ kg}$ ]
  - BMI [<18.5, ≥18.5 to <25.0, ≥25]
  - Onset age [ $\leq 50$  yrs.]  $\geq 50$  yrs.]
  - Duration of disease [ $\leq 5$  yrs.]  $\geq 5$  yrs.]
  - Past treatment with this drug [present, absent]
  - Mutant genotype 2 [with V30M, without V30M]

- Karnofsky performance status [100-80, 70-50, 40-10]
- Family history of TTR-FAP [present, absent]
- Origin of patient [endemic region, non-endemic region]
- Past history of organ transplantation [present, absent]
- Past history of liver transplantation (including for purposes other than the treatment of target disease) [present (including domino liver transplantation), absent] \* Only for safety assessment
- Past history of liver transplantation other than domino liver transplantation [present, absent (including domino liver transplantation)] \* Only for efficacy assessment
- Hepatic impairment [present, absent]
- Hepatic impairment [absent, mild, moderate, severe]
- Renal impairment [present, absent]
- Baseline total NIS score [ $\leq 70$ ,  $\geq 70$ ]
- Baseline NIS-LL score [ $\leq 10$ , >10 to  $\leq 20$ , >20]
- Baseline total QOL (TQOL) score [ $\leq 20$ , >20 to  $\leq 40$ , >40]
- Severity of disease [Stage 1 (walking ability score 0-2), Stage 2 (walking ability score 3a/3b),
   Stage 3 (walking ability score 4)]

Subgroup analysis for mutant genotype will be performed only in patients with a diagnosis of mutant genotype.

- Others
  - Pretreatment (loperamide) [present, absent]
  - Pretreatment (prednisolone) [present, absent]
  - Pretreatment (rosuvastatin) [present, absent]
  - Pretreatment (NSAIDs) [present, absent]
  - Duration of treatment [ $\leq 52$  weeks, >52 to  $\leq 104$  weeks, >104 to  $\leq 156$  weeks, >156 weeks]
  - Concomitant medication (loperamide) [present, absent]
  - Concomitant medication (prednisolone) [present, absent]
  - Concomitant medication (rosuvastatin) [present, absent]
  - Concomitant medication (NSAIDs) [present, absent]

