#### 8.1.2. Categorical variables

For categorical variables, patients falling into each category will be summarized in terms of frequency (n) and proportion.

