## • Others

Summarization will be performed according to Section 8.1 for the following aspects:

- Disposition of concomitant medications (Concomitant medications are defined as drugs recorded in Concomitant Drug Therapies or Pretreatments Used for Target Disease [including NSAIDs etc.] that were used in the period from the start of the treatment with this drug to the discontinuation/end of the treatment. If the treatment with this drug continued exceeding the end of observation, drugs used by the last visit should be eligible.)
- Disposition of concomitant non-drug therapies (Concomitant non-drug therapies are defined as therapies recorded in Concomitant Non-Drug Therapies that were used in the period from the start of the treatment with this drug to the discontinuation/end of the treatment. If the treatment with this drug continued exceeding the end of observation, therapies used by the last visit should be eligible.)
- Disposition of pretreatments (Pretreatments are defined as pretreatments used for target disease [including NSAIDs etc.] or drugs recorded in Concomitant Drug Therapies that were administered before the start of the treatment with this drug.)

Using the SAS, the following aspects of patients will be summarized in terms of n and proportion by system organ class (SOC) and by preferred term (PT):

- Past medical history (diseases or syndromes recorded as "past history" in the medical history)
- Complications (diseases or syndromes recorded as "current history" in the medical history)

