#### 8.2.3.1. Adverse reactions

#### All adverse reactions

Adverse reactions will be summarized by SOC and PT in terms of n and proportion.

In particular, important potential risks, i.e., events related to hepatotoxicity, hypersensitivity reaction, developmental and reproductive toxicity, and infections will be summarized for each event in terms of n and proportion; when n is very small for each event, however, only a listing will be presented in tabular form.

In addition, each of events related to pain in extremity, myalgia, gastrointestinal symptoms, skin, central nervous system, fall, suicide, hepatopathy, thyroid function, vitamin A deficiency, and increased blood glucose will be summarized separately in terms of n and proportion, as necessary.

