## Association between concomitant medication and adverse reactions

To examine the association between a concomitant medication and adverse reactions, patients with any adverse reaction will be summarized by concomitant medication in terms of n. For each patient, concomitant medications used after the last dose should be excluded from consideration.

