## 8.2.3.3. Subgroup analyses

The number and proportion of patients who experienced at least 1 adverse reaction will be tabulated by factor specified in Section 5.4. The evaluation specified in Section 8.1.3 will be performed to evaluate the relationship between patient characteristics and the onset of adverse reactions. In the calculation of risk ratio, the categories to be used as the reference are underlined.

Hepatotoxicity will also be evaluated in the same manner as above if it occurs at a sufficient incidence in the evaluation.

The evaluation specified in Section 8.1.3 will be performed for infection with the presence or absence of liver transplant as a factor.

The number and proportion of patients with adverse reactions will be tabulated by SOC and PT by history of liver transplant. Events related to blood disorder in particular will be examined based on the tabulation results

The number and proportion of patients with adverse reactions will be tabulated by SOC and PT for each category of age [< 15 years,  $\ge$  15 to < 65 years,  $\ge$  65 years], hepatic impairment [Yes, No], and renal impairment [Yes, No]. The number and proportion of patients with adverse reactions in the subgroup of hepatic impairment [severe] will also be tabulated by SOC and PT.

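### The two SAP tables meant to examine association between background drugs and adverse reactions report only reactor counts, which cannot show association on their own

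*SAP*

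**What the plan says.** SAP 8.2.3.1 contains two short subsections on background treatment. The pretreatment one gives its purpose as "To examine the association between a pretreatment and adverse reactions" and its output as "patients with any adverse reaction will be summarized by pretreatment in terms of n". The concomitant-medication one has the parallel purpose, and its output is "patients with any adverse reaction will be summarized by concomitant medication in terms of n"; it also leaves out drugs used after the last dose.

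The main table in the same section is specified differently: "Adverse reactions will be summarized by SOC and PT in terms of n and proportion". The onset-timing table immediately before the two subsections defines its own denominator.

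Two other parts of the SAP bear on the point:

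- **Subgroup analyses.** SAP 8.2.3.3 says: "The number and proportion of patients who experienced at least 1 adverse reaction will be tabulated by factor specified in Section 5.4". The drug factors in 5.4 take the form "Pretreatment (loperamide) [present, absent" and cover loperamide, prednisolone, rosuvastatin and NSAIDs, each as pretreatment and as concomitant medication. SAP 8.1.3 adds a risk ratio with 95% CI, and 5.4 marks absence of the drug as the reference.
- **Disposition of drugs.** For pretreatments and concomitant medications, SAP 8.2.2 (Others) says: "Summarization will be performed according to Section 8.1 for the following aspects". Under 8.1.2 this means that "patients falling into each category will be summarized in terms of frequency (n) and proportion". The instruction to use the safety analysis set (SAS) comes after the drug items and introduces medical history, so the analysis set for the drug tables is not named.

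**The concern.** A table that sets out to examine association needs at least the risk among users and the risk among non-users. These two tables give only the numerator of the first. The SAP elsewhere distinguishes a count from a count with a proportion, so a programmer following the text would produce counts alone.

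For every drug outside the four named drugs or classes, this count is the only by-drug summary of adverse reactions. Protocol 7.3.2.7.1 collects all drugs used during the observation period, so there may be many such drugs. The final analysis supports the reexamination application. A reader of that file could take a large count for a commonly used drug as a signal, or overlook a less common drug whose users react more often.

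**Working it through.** **Inputs.** The documents give no drug-use rate and no adverse reaction rate. The only size figure is the estimated number of patients with TTR-FAP in Japan (SAP 2.1). It reproduces: 0.87 × 127.54 = 110.96 and 1.1 × 127.54 = 140.29, stated as approximately 111 to 140. It is used below only to set a scale; all use and reaction rates are assumptions.

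**Formula.** Let N be the patients analysed, T those with any adverse reaction, U the users of a drug, and n the users with a reaction. The planned entry is n = U × (risk among users). Association is measured by

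RR = (n / U) ÷ ((T − n) / (N − U)).

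N and T can be taken from other planned summaries. U is not in the association tables.

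**Step 1: one entry, several associations.** Assume 20% of patients react and half of the reactors used the drug. Then n = T − n and the formula reduces to RR = (N − U) / U.

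| N | T | n in table | Users U | Risk in users | Risk in non-users | RR |
|---|---|---|---|---|---|---|
| 111 | 22 | 11 | 17 | 11/17 = 65% | 11/94 = 12% | 5.53 |
| 111 | 22 | 11 | 33 | 11/33 = 33% | 11/78 = 14% | 2.36 |
| 111 | 22 | 11 | 56 | 11/56 = 20% | 11/55 = 20% | 0.98 |
| 111 | 22 | 11 | 78 | 11/78 = 14% | 11/33 = 33% | 0.42 |
| 140 | 28 | 14 | 21 | 14/21 = 67% | 14/119 = 12% | 5.67 |
| 140 | 28 | 14 | 42 | 14/42 = 33% | 14/98 = 14% | 2.33 |
| 140 | 28 | 14 | 70 | 14/70 = 20% | 14/70 = 20% | 1.00 |
| 140 | 28 | 14 | 98 | 14/98 = 14% | 14/42 = 33% | 0.43 |

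The same printed number fits a positive, a null or an inverse association.

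**Step 2: equal risks.** Give two drugs the same 20% risk, with 60% and 10% use. At N = 111 the counts are 67 × 0.20 ≈ 13 and 11 × 0.20 ≈ 2. At N = 140 they are 84 × 0.20 ≈ 17 and 14 × 0.20 ≈ 3. Here the difference in counts reflects use alone.

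**Step 3: unequal risks.** A drug used by 60 patients with 15% reacting gives 60 × 0.15 = 9. A drug used by 6 with 50% reacting gives 6 × 0.50 = 3. The count is 9/3 = 3.0 times higher for the first drug, while the proportion is 0.50/0.15 = 3.3 times higher for the second. Use differs 60/6 = 10-fold but the count only 3-fold, so the count is a mixture of use and risk. The exact 95% CIs are about 7% to 27% for 9/60 and 12% to 88% for 3/6. They overlap, so a denominator makes the figures interpretable but not precise.

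**Step 4: would a denominator be enough for concomitant drugs?** Protocol 7.3.2.7.1 has drugs given to treat adverse events entered as concomitant therapy, and records for each drug whether it was given as an action for an adverse event. The SAP subsection removes only use after the last dose. A drug started because of a reaction would therefore count as exposure, and a plain user versus non-user proportion would make it look associated with the reaction it was given to treat.

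**The case against.** The strongest reply is that the plan works in two tiers: a simple count for every drug, and a proper comparison for drugs selected in advance. The SAP revision history supports this. Version 10.0 identified the drugs for subgroup analysis, set absence as the reference category, and removed a statement that risk ratios would not be calculated for them. User counts for the remaining drugs should appear in the 8.2.2 disposition tables, whose definition of concomitant use broadly matches that of the association table, so a crude proportion could be worked out. The study tests no hypothesis (SAP 4.1), and Protocol 7.9 already warns that confounding may not be adequately handled. All of this stands and limits the point.

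It does not remove it. The two subsections do not call for the disposition counts. A reader would have to divide across tables whose analysis set is not stated, then subtract to get the non-user risk.

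Three stronger readings are tempting but not supported:

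- A reader might infer that the tables rank drugs by how often they are used. The SAP prescribes no sort order, and a count follows use alone only when risks are similar.
- A reader might infer that the study cannot answer its own question. Its objective (Protocol 6, SAP 2.2) is long-term safety and efficacy, with hepatotoxicity as the major item; background drugs are not an objective.
- A reader might infer that no comparison by drug is planned. One is, for four named drugs or classes, and SAP 8.2.3.3 is where it is set out.

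**Conclusion.** The point holds in a limited form. In both subsections the planned count mixes use with risk and cannot by itself serve the stated purpose. The gap concerns drugs other than loperamide, prednisolone, rosuvastatin and NSAIDs. It is one of presentation, since the missing denominators should be recoverable from 8.2.2 once the analysis set is fixed.

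The size cannot be stated from the documents. The figures above show only how far the same entry can mislead under assumed use and reaction rates. That a count alone does not determine association does not depend on those assumptions. No hypothesis, endpoint, error rate or sample size is affected, so this is a minor reporting correction.

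**What to change.** In both subsections of SAP 8.2.3.1, replace the count-only output with, for each drug:

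- the number of SAS patients who used it;
- the number and proportion of those users with any adverse reaction;
- the same proportion among SAS patients who did not use it.

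Apply this to drugs above a minimum number of users fixed before analysis (for example 5), and list the rest.

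In the concomitant-medication table, do not count as exposure any drug recorded on the CRF as given to treat an adverse event. Label both comparisons as descriptive and unadjusted.

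The cost is a short change to the SAP text and a few extra columns in two existing tables, with no new data collection. The tables become longer, and cells for less common drugs will be small and imprecise; a threshold as low as 5 limits this only in part.
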